4.2 Objectives

4.2.1 Primary Objective

The primary research objective is to assess the safety of a AAV2/8 vector for h*CNGB3* gene replacement in the retina. Safety is defined as:

Safety is defined as the absence of an ATIMP-related:

- Reduction in visual acuity by 15 ETDRS letters or more
- Severe unresponsive inflammation (defined below)
- Infective endophthalmitis
- Ocular malignancy
- Grade III or above non-ocular SUSAR (see section 5.11.3)

Severe unresponsive inflammation will be defined according to the Standardisation of Uveitis Nomenclature (SUN) Working Group grading system (Jabs *et Al.* 2005) i.e.

- anterior chamber cells 3+ (26-50 cells in a field size of 1mm x 1-mm slit-beam), or
- anterior chamber flare 3+ (marked, iris and lens details hazy), or
- vitreous haze 3+ (Ophthalmology 1985; 92:467-71)

that fails to improve by 2 steps (or to grade 0) during a 6-week period.

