5.4.2.3 Subsequent Assessments

On the first postoperative day a full clinical ocular examination will be performed. In particular, visual acuity, intraocular pressure, the degree of postoperative intraocular inflammation and the area of any residual retinal bleb will be documented. Fundus photography, autofluorescence imaging, ocular examination, intraocular pressure and SD-OCT will be performed at day 1 and each subsequent visit post ATIMP administration.

A standard post-vitreectomy treatment regimen of topical antibiotic (chloramphenicol 0.5% qds for 7 days) and steroid (dexamethasone 0.1% qds for 4 weeks) will be prescribed to minimise inflammation and protect against infection postoperatively.

Intraocular pressure of greater than 30 mmHg will be managed using appropriate ocular antihypertensive therapy.

Participants will be maintained on oral prednisolone (or other as appropriate) for 4 weeks following administration of ATIMP as described above (Section 5.4.2.2.1: Pre-operative procedure). The possible development of steroid-induced adverse effects will be monitored regularly. In particular, blood pressure will be measured and blood glucose, renal function and liver function will be evaluated through blood biochemistry at the time points specific in Table 2: Trial Assessments.

Both safety and efficacy of the ATIMP will be evaluated at various time points up to 6 months after ATIMP delivery. Evaluations will comprise primarily, ocular assessments. The nature and schedule (Section 5.6: Trial Assessments) of these is described below.

(i) Clinical assessment of intraocular inflammation

The degree of intraocular inflammation will be assessed by slit-lamp biomicroscopy at each time point. A temporary intraocular inflammatory response is expected following vitrectomy surgery. This is typically evident clinically on slit-lamp biomicroscopy as 'flare' and cells in the anterior chamber and can be of moderate (2+ cells) intensity. The degree of intraocular inflammation is expected to decline over the course of the first 4 weeks following the surgical procedure, at which time the routine topical and systemic immunosuppression will be discontinued. Prolonged or severe intraocular inflammation, or deterioration in visual acuity that may be related to intraocular inflammation, will be investigated and managed conventionally with further topical and/or systemic immunosuppression.

(ii) Evaluation of immune responses

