2. OUTCOME DEFINITIONS

2.1. Primary Safety Outcome

The primary safety outcome is defined as any of the below events occurring during the 6 weeks following administration, at least possibly related to the ATIMP, not surgery alone:

• Reduction in visual acuity by 15 Early Treatment Diabetic Retinopathy Study (ETDRS) letters or more

- Severe unresponsive inflammation (defined in Section 4.2 of the protocol)
- Infective endophthalmitis
- Ocular malignancy
- Grade III or above non-ocular suspected unexpected serious adverse reaction (SUSAR) (Protocol MGT006, Section 5.11.3.4.2 Severity or Grading of Adverse Events).

This is the same criteria as the dose limiting event in the dose escalation phase.

Overall safety will be assessed for 6 months after the intervention in this study, and a further 4.5 years in a separate long-term follow-up study (Protocol MGT007).

The adverse events preferred terms are identified in a separate file (AES_OF_INTEREST.xlsx) and saved in the ERIS system.

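### Severe unresponsive inflammation is fixed at grade 3+, with cells capped at 50 and no upward extension, so the component can miss a worse eye in which no sign is ever graded exactly 3+

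*Protocol*

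**What the plan says.** Protocol 4.2.1 lists five safety components. It spells out severe unresponsive inflammation as any one of three signs:

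- for cells, the criterion reads "anterior chamber cells 3+ (26-50 cells in a field size of 1mm x 1-mm slit-beam), or"
- flare graded 3+, described in words and without a numerical range
- haze of the vitreous graded 3+, defined by a literature citation and likewise without a range

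The sign must also be one "that fails to improve by 2 steps (or to grade 0) during a 6-week period".

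Two neighbouring components in the same list are open at the top: "Reduction in visual acuity by 15 ETDRS letters or more" and "Grade III or above non-ocular SUSAR (see section 5.11.3".

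Protocol 4.3.2.1 repeats the inflammation definition word for word for the DLE. Protocol 5.5.1 and 5.10.3.2 name the component without defining it again. SAP 2.1 points back to the protocol, "Severe unresponsive inflammation (defined in Section 4.2 of the protocol", adds no threshold of its own, and says that the outcome and the DLE use the same criteria.

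Elsewhere, Protocol 5.4.2.3 says that expected postoperative inflammation "can be of moderate (2+ cells) intensity".

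**The concern.** A severity threshold in a safety outcome should keep applying as the event gets worse. Here the list is introduced as a definition (i.e.), not as examples. It names one grade, and for cells it gives that grade a numerical ceiling. Followed exactly, a non-responding eye with 40 cells meets the cell criterion and one with 60 does not.

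The component is there to capture severe inflammation that does not respond to treatment. A gap at its upper end would understate the primary outcome in the eyes where it matters most. The same wording defines the DLE, and the groups are small. In Table 1 of Protocol 4.3.2.2.4, 0/3 and 1/3 DLEs lead to different actions at the low and intermediate doses. SAP 5.1 reports proportions by age group and dose level, so one reclassified eye is visible in the results.

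**Working it through.** The plan states no figure on this point, so there is none to reproduce. The check compares the passages and then counts the patterns that the literal wording misses.

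**1. Does the plus sign mean 'or more'?** Protocol 5.4.2.3 uses 2+ as the label for moderate intensity, so 3+ reads as a grade. The 26-50 range confirms this for cells, since an open-ended criterion would have no ceiling. Protocol 4.3 does use the sign in the other sense for ages (16+ and 18+). The symbol therefore has two meanings in the protocol and cannot settle the matter alone.

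**2. Does any other passage extend the threshold upward?** Protocol 4.2.1, 4.3.2.1, 5.5.1 and 5.10.3.2 and SAP 2.1 do not.

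**3. Which grade patterns are missed?** Put each of the three signs (cells, flare, haze) below 3+, at 3+ or above 3+. That gives 3 × 3 × 3 = 27 patterns at a single assessment.

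- With 3+ or above, a pattern reaches the severity threshold unless all three signs are below 3+: 27 − 1 = 26.
- Read literally, at least one sign must be exactly 3+. Patterns with none at 3+ number 2 × 2 × 2 = 8, so 27 − 8 = 19 qualify.
- Missed: 26 − 19 = 7.
- Cells above the band: 3 × 3 = 9 patterns. Of these, 2 × 2 = 4 have neither flare nor haze at 3+ and are missed; the other 5 still qualify.

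This assumes that flare and haze have grades above 3+, which the documents do not show. If they have none, there are 3 × 2 × 2 = 12 patterns. Eleven reach the threshold with 'or above' and 10 read literally. The one missed pattern has cells above the band and both other signs below 3+. That is 1 of the 4 patterns with cells above the band.

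These are counts of patterns, not probabilities.

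**4. What about repeated visits?** Protocol Table 2 schedules ocular examination at days 1 and 3 and weeks 1, 2, 4 and 6. An eye graded 3+ at one visit that then worsens has failed to improve and meets the component. The gap therefore needs an eye in which no sign is graded exactly 3+ at any visit.

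**5. How large is one missed eye?** 1/3 = 33.3% in a cohort of 3; 1/36 = 2.8% if all 36 participants are treated.

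**6. How often could it happen?** Protocol 4.1.5.1 reports transient inflammation in 3 of 12 participants in the first trial, and posterior-segment episodes in a minority in the second. It gives no grades, so no rate can be derived.

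**The case against.** The strongest reply is that nobody would read the text this way. The component is named for severe inflammation that does not respond, and a clinician or the IDMC would very likely count a worse eye. The IDMC also reviews safety data before each escalation, and SAP 5.2 summarises and lists ocular inflammation events of interest separately, so the eye would not vanish from the report. This stands as a reason to expect little practical effect. It does not supply the missing words in a pre-specified primary outcome.

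Several stronger readings that a reader might infer are not supported:

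- *Eyes worse than the band cannot meet the primary outcome.* They can, through flare or haze at 3+, through a 3+ grade at another visit, or through another component such as the 15-letter loss.
- *Every eye above 50 cells is excluded.* SAP 3.5 analyses a value recorded as greater than x as x. A count entered as >50 would become 50, inside the band. The documents do not say how counts are recorded.
- *The SAP tells the analyst to select recorded grade 3+ only.* It gives no such rule. SAP 2.1 refers to a separate file of adverse event preferred terms, and the outcome also needs a judgement that the event is at least possibly related to the product. The SAP simply leaves the inequality unstated.
- *Protocol 4.1.5.1 ranks inflammation as the main vector risk.* That section says when inflammation is most likely; it does not rank it against other risks.

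**Conclusion.** The narrow point holds. As written, an eye with more than 50 anterior chamber cells does not meet the cell criterion, and the inflammation component misses it if no sign is ever graded exactly 3+. It may still count as a primary outcome event by another route. The wording is shared by the primary outcome and the DLE, and the SAP does not repair it.

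The intent is very likely 3+ or worse, so this is a drafting error with an uncontroversial correction. Its frequency is unknown and probably low, and no effect on the expected event rate is claimed.

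The conclusion rests on reading 3+ as a grade label and on taking a grade above it to exist. For cells, that grade is inferred from the ceiling of 50. For flare and haze it cannot be shown from the documents, which do not reproduce the grading scales.

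**What to change.** In SAP 2.1, state that the primary safety outcome counts grade 3+ or above for anterior chamber cells, flare and vitreous haze, with the non-improvement clause unchanged. Check the ocular examination listings for any eye graded above 3+ and confirm how it was classified.

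The SAP describes the conduct of the trial in the past tense, so the analysis definition is the practical place for the change. SAP 2.1 says that the outcome and the DLE use the same criteria, so Protocol 4.2.1, Protocol 4.3.2.1 and SAP 2.1 must be reconciled. This point proposes no escalation threshold.

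The cost is one sentence in the SAP, one explicit inequality wherever the grade is used, and a review of data already collected. No new visits or measurements are needed. The event count can only stay the same or rise, provided that a 3+ grade that starts the non-improvement assessment now still does so.

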4.2.2 Secondary Objective

The secondary research objective is to determine whether a AAV2/8 vector for h*CNGB3* gene replacement in the retina can improve retinal function, visual function and quality of life.

4.3 Trial Design

This is an open-label phase I/II dose-escalation trial to determine the safety and efficacy of subretinal administration of the ATIMP in participants with *CNGB3*-related achromatopsia.

In the dose escalation phase, up to 18 adult participants will be administered a single dose of the ATIMP in cohorts of 3 participants at a time. Based on toxicity data, the IDMC will make a

Gene Therapy for Achromatopsia (CNGB3)

recommendation on the dose to administer to the next cohort of 3 participants. The IDMC may recommend additional participants at a given dose before deciding how to proceed.

Adults are defined as participants aged 16+ in the UK and aged 18+ in the US.

Once an acceptable safety profile has been established in adults, up to 18 additional participants, who may be children or adults, will be included. The IDMC will agree the maximum tolerated dose in adults before recommending administering up to this dose in the expansion phase.

Safety and efficacy will be assessed for 6 months following the intervention by clinical examination and special investigations according to the schedule in section 5.6 of the protocol.

4.3.1.1 Separate longer term follow up study

Safety will be assessed on an ongoing basis in this study. When the 6 months follow up time point has been reached in this study, participants will subsequently be invited to enrol in a separate follow-up study where they will be assessed for safety up to 60 months following ATIMP administration. The duration of long-term follow-up is therefore consistent with the recommendations of the current CHMP Guideline on Follow-up of Patients Administered with Gene Therapy Medicinal Products (EMA/CHMP/GTWP/60436/2007) of 22 October 2009, where it is stated that, for viral vectors without integration, latency or reactivation potential, a brief clinical history and sample testing should be performed pre-treatment, at 3, 6 and 12 months after treatment, and then yearly thereafter for a minimum of 5 years (and, if non-clinical tests or evidence from other clinical trials using identical vectors or modifications of vectors indicate a potential for integration or late re-activation, the monitoring should be extended to continue yearly after those 5 years until data indicate that there is no longer any risk to be followed). Further, although the FDA Guidance for Industry: Gene Therapy Clinical Trials – Observing Subjects for Delayed Adverse Events (November 2006) recommends a standard 15-year period of follow-up, it is also noted that a shorter period of follow up may be appropriate if the ATIMP does not integrate and has no potential for latency and reactivation.

The follow-up study will be a non-intervention study designed to collect data on longer term safety and efficacy at the equivalent of 9, 12, 18, 24, 36, 48 and 60 months following ATIMP administration; as such, participants in both studies will be followed up more frequently than recommended in the guidance, as additional assessments following ATIMP administration are included in the initial study (at weeks 1, 2, 4 and 6) and in the long-term follow up study (at months 9 and 18). The follow up study will have a separate protocol, participant information and consent process, and will be submitted for separate ethical review. Participants in the current study will be strongly encouraged to join the follow up study as part of their ongoing clinical review, but there will be no obligation on their part to do so. It is acknowledged that, despite encouragement, participants may elect not to participate in the long-term follow-up study; however, in this motivated population, where individuals are typically monitored by their specialist closely and regularly, this is considered unlikely.

Gene Therapy for Achromatopsia (CNGB3)

4.3.2 IMP administration Review and Dose Escalation Criteria and Process

Up to 18 adult participants (as defined in section 4.3) will be administered a single dose of ATIMP in a total volume of 0.5mL, according to the dose-escalation criteria:

- 1) low dose [REDACTED]
- 2) intermediate dose [REDACTED]
- 3) high dose [REDACTED]

Once a maximal tolerated dose is established, up to 18 further participants aged 3 years or older will continue to be administered vector up to the highest dose observed to be tolerated in adults.

In order to explore optimal dosing within safe limits ([REDACTED]), additional doses may be administered in order to maximise therapeutic effect, whilst maintaining the safety profile of the product. Any dose that differs from those described above will not exceed the highest titre of [REDACTED]. The Chief Investigator, Medical Monitor and IDMC chair will confirm additional doses and participant numbers in advance of them being administered. The actual titre to be administered will be recorded in the eCRF.

4.3.2.1 Dose escalation criteria and Dose Limiting Events

Dose escalation will be undertaken in adults, based on an escalation rule around dose-limiting events (DLEs). An IDMC will review data from a minimum of 6 weeks of follow up from each cohort of 3 participants, before recommending the next dose to be assessed in a further cohort of patients.

A DLE is defined as any of the below occurring during the 6 weeks following administration, at least possibly related to the ATIMP, not surgery alone:

- Reduction in visual acuity by 15 ETDRS letters or more
- Severe unresponsive inflammation (defined below)
- Infective endophthalmitis
- Ocular malignancy
- Grade III or above non-ocular SUSAR (see section 5.11.3)

Severe unresponsive inflammation will be defined according to the Standardisation of Uveitis Nomenclature (SUN) Working Group grading system (Jabs *et Al.* 2005) i.e.

- anterior chamber cells 3+ (26-50 cells in a field size of 1mm x 1-mm slit-beam), or
- anterior chamber flare 3+ (marked, iris and lens details hazy), or
- vitreous haze 3+ (Ophthalmology 1985; 92:467-71)

that fails to improve by 2 steps (or to grade 0) during a 6-week period.

Review of safety data will be undertaken by the IDMC prior to each dose escalation. Children will be included at up to the highest safe ATIMP dose recommended by the IDMC, once a safety profile has been established in adult participants according to the dose escalation rules.

4.3.2.2 Dosing process

4.3.2.2.1 Cohort 1

ATIMP will first be administered at the lowest dose to one adult participant only. This participant will be monitored for signs of toxicity for a period of 6 weeks. If there is no DLE as defined above after a minimum of 6 weeks, ATIMP will continue to be administered at the same dose to 2 further adult participants. In the event of a DLE in the first adult in the cohort, a discussion will be held with the IDMC to agree a plan of action for administering the ATIMP to further adults. The IDMC will review the data collected on this cohort up to 6 weeks following ATIMP administration to the 3rd participant.

4.3.2.2.2 Cohort 2

In the event that there is no DLE in any participant, the IDMC will recommend administering ATIMP at the intermediate dose level to a single adult participant. If there is no DLE after a minimum of 6 weeks, ATIMP will continue to be administered at the same dose to 2 further adult participants. In the event of a DLE in the first adult in the cohort, a discussion will be held with the IDMC to agree a plan of action for administering the ATIMP to further adults. The IDMC will again review the data available on this next cohort of adult participants up to 6 weeks following ATIMP administration to the 3rd participant.

4.3.2.2.3 Cohort 3

In the event that there is no DLE in any participant, the IDMC may recommend administering ATIMP at the highest dose level to a single adult participant. If there is no DLE after a minimum of 6 weeks, ATIMP will be administered at the same dose to 2 further adult participants. In the event of a DLE in the first adult in the cohort, a discussion will be held with the IDMC to agree a plan of action for administering the ATIMP to further adults.

4.3.2.2.4 Additional considerations

In the event of a DLE in one of the 3 participants at a given dose, the cohort will be expanded at the same dose level. The IDMC will review the safety data and confirm that additional participants may be treated at this dose. The IDMC may recommend that the same dose of ATIMP is administered to additional participants. The dose escalation will continue until IDMC are comfortable on review of the accumulating data, to recommend a maximum dose to be administered to children, or 3 participants have been administered the highest dose without any DLEs, or until at least 2 participants among a cohort of 3 to 6 participants experience DLEs (i.e., $\geq 33\%$ of patients with a DLE at that dose level), in which case the recommended dose will be the level below this toxic dose. In the event that 1 or 2 DLEs are seen at the first dose level, the IDMC may recommend administering a lower dose to that described in the protocol to a cohort of participants.

Table 1: Dose escalation table

Number of DLEs			
Low dose			
Participants 1-3	Participants 4-6	Action	Details
0/3		Increase	Give intermediate dose to next cohort of participants
1/3		Remain	Give low dose to another cohort of participants (Pt 4-6)
$\geq 2/3$		Stop	MTD not found. Consider lower dose
	$\leq 1/6$	Increase/stop	Has higher dose been tried? No: Give intermediate dose to next cohort of participants

Gene Therapy for Achromatopsia (CNGB3)

			Yes: MTD found – low dose
	≥ 2/6	Stop	MTD not found. Consider lower dose
Intermediate dose			
Participants 1-3	Participants 4-6	Action	Details
0/3		Increase	Give high dose to next cohort of participants
1/3		Remain	Give intermediate dose to participants 4-6
≥ 2/3		Decrease/stop	Give low dose to 3 more participants. If 6 participants already had low dose, stop. MTD found – low dose.
	≤ 1/6	Increase/stop	Has higher dose been tried? No: Give high dose to participants 1-3 Yes: MTD found – intermediate dose
	≥ 2/6	Decrease/stop	Give low dose to participants 4-6. If 6 participants already had low dose, stop. MTD found – low dose
High dose			
Participants 1-3	Participants 4-6	Action	Details
0/3		Remain	MTD found – give high dose to participants in confirmation phase
1/3		Remain	Give high dose to participants 4-6
≥ 2/3		Decrease/stop	Give intermediate dose to participants 4-6. If 6 participants already had intermediate dose, stop. MTD found – intermediate dose
	1/6	Stop	MTD found – high dose
	≥ 2/6	Decrease/Stop	Give intermediate dose to participants 4-6. If 6 participants already had intermediate dose, stop. MTD found – intermediate dose

4.3.2.2.5 Confirmatory safety phase

MeiraGTx UK II Ltd. will seek IDMC agreement on the highest dose that can be administered in the expansion cohort. This may include up to 18 participants who may be adults or children.

Recruitment into this expansion cohort can begin at any dose level up to the IDMC agreed highest dose level. Children are defined as those aged 15 and under in the UK and 17 and under in the US. Children will be administered up to the maximal tolerated dose determined in adults. Having identified a group of children who may be willing to participate in the study, the CI will prioritise ATIMP administration to older candidates in the first instance. The first child administered ATIMP will be monitored for safety for a period of 6 weeks. If there is no adverse event consistent with the above definition of a DLE after 6 weeks, ATIMP will continue to be administered to up to 17 further participants. In the event of an AE as described above in the first child, a discussion will be held with the IDMC to agree a plan of action for administering the ATIMP to further children.

5 Methods

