5.4.9.2 Trial Stopping Rules

The Chief Investigator and Sponsor retain the right to terminate the study. Specific circumstances that may precipitate such termination are as follows:

1. Unanticipated severe adverse event in this or other studies indicating a potential health hazard caused by the ATIMP
2. Significant protocol deviation and lack of compliance and cooperation on the part of an investigator, which endangers the safety of the participants or the validity of the study
3. Death of a participant at any time point after ATIMP administration that is possibly, probably, or definitely related to the ATIMP
4. The occurrence of a non-ocular malignancy at any point after gene transfer that is possibly, probably, or definitely related to the ATIMP

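### In the expansion phase the protocol requires IDMC involvement only after an event in the first child; a DLE-type event in any other participant triggers no required IDMC review or pause.

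*Protocol*

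**What the plan says.** **Expansion (Protocol 4.3.2.2.5).** The phase takes up to 18 adults or children, at doses up to the highest that the IDMC agrees. The first child is watched for 6 weeks. If there is no event of the DLE type, the protocol states: "after 6 weeks, ATIMP will continue to be administered to up to 17 further participants". If there is one: "In the event of an AE as described above in the first child, a discussion will be held with the IDMC", and that discussion concerns dosing of further children. The section gives no step for an event in a later child or in an adult.

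**Escalation (4.3.2.2.1 to 4.3.2.2.4).** The first adult in each cohort has a similar step: "In the event of a DLE in the first adult in the cohort, a discussion will be held with the IDMC". A second and firmer step then applies to the cohort. After a DLE in one of 3 participants at a dose, "The IDMC will review the safety data and confirm that additional participants may be treated at this dose". Two or more DLEs among 3 to 6 participants make the dose too toxic (4.3.2.2.4 and Table 1).

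**Definition (4.3.2.1).** "A DLE is defined as any of the below occurring during the 6 weeks following administration", and at least possibly related to the ATIMP rather than to surgery alone. The list covers acuity loss of 15 letters or more, severe unresponsive inflammation, infective endophthalmitis, ocular malignancy and severe non-ocular SUSARs.

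**Stopping (5.4.9.2).** The Chief Investigator and sponsor keep a right to terminate. The list of reasons opens with "Specific circumstances that may precipitate such termination are as follows".

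**The concern.** The expansion phase carries over the sentinel step from escalation, for one child, but not the firmer step that follows it. A site could follow 4.3.2.2.5 to the letter, see an event that meets the DLE definition in, say, the fifth participant, and dose the sixth without the IDMC having looked at the case.

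This is the phase that admits children from age 3, and its own title calls it a confirmatory safety phase. It may start on little adult data: Table 1 accepts 0 DLEs in 3 participants at the high dose as enough to declare the maximum tolerated dose. At stake is whether a listed safety failure in this phase must be considered by the independent committee before the next participant is treated, or only may be.

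**Working it through.** The plan states no figure on this point, and 5.7 says there is no formal sample size calculation. The check is a comparison of rules plus a headcount.

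**1. Required IDMC action after a DLE-type event**

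| Who has the event | Escalation | Expansion |
|---|---|---|
| First participant of the cohort | Discussion with the IDMC (4.3.2.2.1 to 4.3.2.2.3) | Discussion, if this is the first child (4.3.2.2.5); nothing written for a first adult |
| One of 3 at a dose | IDMC reviews and confirms that more may be treated (4.3.2.2.4) | Nothing written |
| Two or more of 3 to 6 | Dose judged too toxic (4.3.2.2.4, Table 1) | Nothing written |

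The rule in 4.3.2.2.4 does not carry over on its own terms. It is framed around 3 participants at a dose and expansion to 6, whereas the expansion phase is not divided into cohorts of 3.

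**2. Headcount**

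Inputs from 4.3.2.2.5: up to 18 participants, one sentinel child, up to 17 further participants.
- Check: 1 + 17 = 18.
- Outside the trigger if any child is enrolled: 17/18 = 94%.
- Outside the trigger if none is: 18/18 = 100%.

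**3. Does another control require a pause or an IDMC review after an event?**

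- 5.11.1: IDMC recommendations are required before dose changes in escalation and before the first expansion participant. Neither is tied to an event in expansion.
- 5.11.2: periodic IDMC reports, on a schedule left to the charter.
- 5.11.4.4.2: a general IDMC remit to watch accumulating data, with no trigger given.
- 5.11.3.2 and 5.11.3.5: prompt review of safety events, with adverse events entered for monitoring by the Clinical Management Team. No dosing action is stated.
- 5.11.3.5 and 5.11.3.6.1: SAE notification within 24 hours. 5.11.3.5.4: any related SAE is treated as a SUSAR and reported to regulators, ethics and biosafety bodies. The IDMC is not named in that route. A DLE also need not be serious: a possibly related 15-letter loss is a DLE, but might not meet a seriousness criterion in Table 3.
- 5.11.3.6.2: urgent safety measures are permitted, not required.
- 5.4.9.2: termination is discretionary, names no IDMC step and does not list the DLE criteria as such.
- SAP 2.1 and 5.1: the same events form the primary safety outcome, but the SAP adds no monitoring rule.

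Each control makes it likelier that someone acts. None obliges a hold or an IDMC review before the next dose.

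**The case against.** The strongest reply is that the rule may exist elsewhere. Section 5.11.1 sends the IDMC's decision process, review timing and any stopping guidelines to its charter. If the charter requires a hold, what remains is a question of where the rule is written. That stands, and it limits the claim to the protocol text.

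Second, escalation is not as strict as a reader might infer from the comparison. Once the first adult passes 6 weeks, two more may be dosed, and no hold on the third is written if the second has a DLE. Nor is there one within participants 4 to 6. Escalation therefore does not stop dosing after every event, and a hold after any single event in expansion goes somewhat beyond parity. That also stands. What survives is that escalation requires IDMC confirmation once one of 3 has a DLE, and expansion has no counterpart.

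Third, one event among 17 would not by itself show an intolerable dose on the trial's own standard of at least 2 DLEs in up to 6 (2/6 = 33%). That is correct, but even in escalation a single DLE prompts review and confirmation, which is all that is asked for here.

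Fourth, further safeguards exist. Older children are dosed first (4.3.2.2.5), and the Chief Investigator, Medical Monitor and IDMC chair confirm additional doses and participant numbers in advance (4.3.2). These reduce risk but do not respond to an event.

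Finally, the SAP describes the expansion participants in the past tense (SAP 1.2), so dosing may be over and an amendment may protect nobody. That changes the form of the remedy. SAP 5.1 already tabulates and lists the events; whether dosing was paused or the IDMC consulted is not among the planned outputs.

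**Conclusion.** The point holds for the protocol text. The only event-triggered IDMC step in expansion covers the first child for 6 weeks. Up to 17 further participants, and every adult in the cohort, fall outside it, while escalation requires IDMC review and confirmation after a DLE in one of 3. It is worth correcting, with medium confidence, because the charter could not be checked.

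Three stronger readings are tempting and not supported:

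- *That expansion runs without safety oversight.* It does not: the controls above apply throughout, and the IDMC may recommend against continuing at any time. The gap is the absence of a required step.
- *That the number of participants exposed after an event, or the chance of such an event, can be stated.* The documents give no DLE rate, no interval between IDMC reports and no recruitment rate for this phase. The 94% is a headcount and says nothing about how likely an event is.
- *That ocular malignancy escapes the stopping rules*, because item 4 of 5.4.9.2 reads "The occurrence of a non-ocular malignancy at any point after gene transfer that is possibly, probably, or definitely related to the ATIMP". Item 1, "Unanticipated severe adverse event in this or other studies indicating a potential health hazard caused by the ATIMP", plausibly covers an ocular one. Ocular malignancy is also on the DLE list, with the same 6-week window in both phases. It is a separate matter and adds nothing to this point.

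**What to change.** Add at the end of Protocol 4.3.2.2.5:

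> If any participant in this phase has an event that meets the DLE definition in 4.3.2.1, no further participant will receive ATIMP at that dose or higher until the IDMC has reviewed the safety data and confirmed that dosing may continue.

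If the IDMC charter already holds a rule for this phase, state that rule in 4.3.2.2.5 instead.

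The cost is one sentence in an amendment, and a delay to recruitment only if an event occurs.

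If dosing is complete, put a short paragraph in the study report instead: whether any DLE-type event occurred in an expansion participant, adult or child, and whether it led to IDMC review or a pause in dosing.
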